3.3 Study drug dosing schedule

Study drugs will be shipped to each clinical center's pharmacy. The research pharmacy staff will then provide the study staff with masked study drug bottles based on the DCC randomization schedule. Patients will be dispensed bottles labeled "Cysteamine bitartrate delayed-release 75 mg capsules or placebo". Study drug should be taken 30 minutes prior to a meal.

Patients will be on a dose escalation regimen, the number of capsules taken will be increased gradually during weeks 1-4 to the assigned number and remain fixed thereafter regardless of weight changes according to the following schemes:

For patients with a baseline weight of 65 kg or less:

- Week 1: One 75 mg capsules orally twice a day (1 in the morning and 1 in the evening) (150 mg/day),
- Week 2: Two 75 mg capsules orally twice a day (2 in the morning and 2 in the evening (300 mg /day)
- Week 3: Three 75 mg capsules orally twice a day (3 in the morning and 3 in the evening) (450 mg/day)
- Weeks 4-52: Four 75 mg capsules orally twice a day (4 in the morning and 4 in the evening) (600 mg/day)

For patients with a baseline weight greater than 65 kg up to 80 kg:

- Week 1: Two 75 mg capsules orally twice a day (2 in the morning and 2 in the evening) (300 mg /day)
- Week 2: Three 75 mg capsules orally twice a day (3 in the morning and 3 in the evening) (450 mg/day)
- Week 3: Four 75 mg capsules orally twice a day (4 in the morning and 4 in the evening) (600 mg/day)
- Weeks 4-52: Five 75 mg capsules orally twice a day (5 in the morning and 5 in the evening) (750 mg/day)

For patients with a baseline weight greater than 80 kg:

- Week 1: Three 75 mg capsules orally twice a day (3 in the morning and 3 in the evening) (450 mg/day)
- Week 2: Four 75 mg capsules orally twice a day (4 in the morning and 4 in the evening) (600 mg/day)
- Week 3: Five 75 mg capsules orally twice a day (5 in the morning and 5 in the evening) (750 mg/day)
- Weeks 4-52: Six 75 mg capsules orally twice a day (6 in the morning and 6 in the evening) (900 mg/day)

3.3.1 Cysteamine DR

Cysteamine DR will be taken orally twice daily 30 minutes prior to meals (morning/breakfast and evening/dinner) for weeks 1-52. The rationale for the 9 mg/kg to 12 mg/kg daily dose range of cysteamine DR is that this target dose was the best tolerated in the pilot study and had the greatest benefit ⁶⁰.

3.3.2 Rationale for a placebo group

Lifestyle interventions are considered the standard treatment for NAFLD, but are often not available to children with NAFLD due to both the lack of available care and limitations of insurance coverage for lifestyle interventions. In this study we will provide all participants, including those receiving placebo with a standardized nutrition and exercise intervention consistent with the recommendations of the American Academy of Pediatrics. Thus all children will receive treatment.

Currently, there are no FDA approved therapies for NAFLD in children. Medications that are being investigated for the treatment of NAFLD cannot be compared with an active alternative treatment arm. In order to assess the efficacy of an agent in NAFLD, a placebo-arm is needed to determine its relative efficacy in improving liver histology beyond that achieved with a placebo. Previous non-randomized and pilot studies have shown the efficacy of several agents such as ursodiol and betaine in the treatment of NAFLD, but follow-up randomized-placebo-controlled studies failed

Confidential, not for distribution to show improvement in liver histology beyond that observed in placebo groups.^{61,62} In order to have the highest quality of evidence to test our hypothesis, the CyNCh trial utilizes a randomized, double-masked, placebo-controlled study design (http://www.ahrq.gov/clinic/uspstf/grades.htm). As there is no proven pharmacologic therapy for NAFLD in children, using a placebo for comparative purposes is justified.

Rationale for a 90 day maximum duration between liver biopsy and registration

Liver histology, especially steatosis, may change over time. A 90-day window provides for adequate time to screen eligible patients but minimizes the likelihood of changes in liver histology before the start of treatment.

3.4 Standard treatment recommendations

The use of prescription or non-prescription medicines or herbal remedies or dietary supplements, consumption of alcohol, and management of various co-morbid illnesses will be discussed with the patients. These recommendations have been prepared by the NASH CRN Pediatric Standard of Care Committee and are approved by the NASH CRN Steering Committee to be applied across all study sites. This will help ensure that the patients in both groups receive the same standard of care treatment for NAFLD.

Enhanced Lifestyle Intervention

All children, including those in the placebo group will receive an intervention in the form of standardized lifestyle intervention recommendations consistent with the latest recommendations from the American Academy of Pediatrics (AAP). Assessing the impact of such an intervention on NAFLD will be important. Attaining a healthy weight is the cornerstone of current treatment of pediatric NAFLD, given the lack of proven pharmaceutical therapy in this age group and the strong association of NAFLD with excess adiposity, in particular central adiposity.⁶³ Weight loss has been associated with improvements in liver enzymes and histology in adults with NAFLD, while weight loss in children with NAFLD has been shown to improve serum aminotransferase levels in small pilot studies.^{36,64,65} Therefore, lifestyle intervention through changes in diet and exercise will be encouraged for participants in both the placebo and active study drug treatment group of the CyNCh trial, as this represents the current standard of care for children.

The standard of care lifestyle intervention designed for this trial will incorporate components of the AAP's 2007 Expert Committee Recommendations Regarding the Prevention, Assessment, and Treatment of Child and Adolescent Overweight and Obesity that can be reproduced across the study sites.⁶⁶ CyNCh Trial participants will be given written materials that will include evidence-based strategies to achieve a healthier diet and increase physical activity, as endorsed by the American Academy of Pediatrics as well as the CDC and NIH.⁶⁴⁻⁶⁸ A family-based, patient-centered and stepped approach to making lifestyle changes will be employed as recommended by the AAP.⁶⁶ Accordingly, the lifestyle materials will be reviewed with trial participants and their family members at each study visit and they will be encouraged to select 1-2 goals which they consider personally obtainable and that they can commit to pursuing in the interval until their next study visit.

Topics to be covered in the materials will include:

- 1) Reduce fat intake and sugar intake to 0 servings per day
- 2) Reduce screen time to 2 hours or less per day
- 3) Increase physical activity to 1 hour or more per day
- 4) Increase fruits and vegetable intake to 5 or more servings per day
- 5) Reduce fast food intake and make healthier choices when eating out

Confidential, not for distribution

These topics and the specific strategies to be included in the lifestyle intervention materials are in accordance with healthy weight strategies currently recommended by the Centers for Disease Control and Prevention and the National Institutes of Health National Heart Lung and Blood Institute's "We Can" program.⁶⁷⁻⁷⁰ Therefore, we will also include references in the study's lifestyle intervention materials to these freely accessible, federal government sponsored websites so that participants and their families can easily access additional information on these lifestyle changes and strategies to achieve them.

Treatment duration-rationale for 52 weeks

An ideal duration of a treatment should only expose participants to a study drug long enough to show meaningful improvement in liver histology if it is going to occur. This enables any positive findings to be reported as soon as possible.

3.5 Primary outcome measure

Centrally scored and masked assessment of histologic improvement in NAFLD between the baseline liver biopsy and follow-up biopsy after 52 weeks of treatment, where improvement is defined as: (1) decrease in NAS of 2 or more and (2) no worsening of fibrosis.

Justification for performing an end-of-treatment liver biopsy:

NAFLD is a clinicopathologic entity and liver biopsy characteristics are required for the diagnosis of NAFLD, the determination of NASH, and the staging of fibrosis. Currently, there are no non-invasive markers to diagnose or grade NASH. Therefore, a liver biopsy is needed to document improvement or worsening. Several of the histologic features of NAFLD including ballooning degeneration and fibrosis have prognostic significance and predict liver-related deaths in patients with NAFLD. Therefore, documentation of improvement of the pathologic lesions of NASH in liver biopsy is needed to show efficacy in a clinical trial.

Rationale for using the NAS:

The primary outcome measure requires improvement in disease activity after 52 weeks of treatment as determined by liver biopsies pre- and post-treatment. The measure is derived from changes from baseline to the end of treatment in the NAFLD activity score (NAS).⁷⁰ The NAS ranges from 0 to 8 (highest activity) and is calculated as the sum of three components of the standardized histologic feature scoring system for liver biopsies:

- NAS = Steatosis (0-3)
- + Lobular inflammation (0-3)
- + Hepatocyte ballooning (0-2)

The NAS provides a semi-quantitative tool to assess treatment response in a clinical trial. It has been validated and this measure is considered a gold standard in the field. It was utilized to assess the efficacy in the NIDDK PIVENS (IND 69,751) and TONIC (IND 71,217) trials conducted by the NASH CRN.⁴⁸ This would also provide a tool to compare the findings across various treatment trials within and outside the NASH CRN. Therefore, we believe that the NAS provides the most objective and reproducible measurement that is available to assess efficacy of treatment in NAFLD.

3.6 Secondary outcome measures (see section 7.2 for details)

Individual histological characteristics

• Change in NAS after 52 weeks of treatment compared to baseline NAS.

Confidential, not for distribution

Changes in fibrosis, steatosis, lobular inflammation, ballooning, and other specific features from the histologic scoring system after 52 weeks of treatment compared to baseline. Improvement in specific features will be defined as any improvement in the NAS.

• Presence or absence of a diagnosis of NASH in the follow-up biopsy

Laboratory

- Aminotransferases
- Normalization of ALT and AST after the end of treatment
- Time-dependent decline in serum mean ALT and AST
- Change in insulin sensitivity
- Markers of oxidation and anti-oxidant status before and after treatment will be compared between groups.

Imaging

• Change in MRI-determined liver fat fraction from baseline to end of treatment

Symptoms and exam

- Changes in Pediatric Quality of Life
- Changes in anthropometric measures

4. Patient selection

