4.2 Inclusion criteria

Patients must satisfy all of the following criteria to be eligible for enrollment:

- Children age 8-17 years inclusive.
- Liver biopsy within 90 days of screening visit and not more than 120 days before randomization.
- Clinical history consistent with NAFLD.
- Definite NAFLD based upon liver histology.
- No evidence of any other liver disease by clinical history or histological evaluation
- A histological severity of NAFLD Activity Score (NAS) \geq 4.
- Sexually active female participants of childbearing potential (i.e., not surgically sterile [defined as tubal ligation, hysterectomy, or bilateral oophorectomy) must agree to utilize the same two acceptable forms of contraception from screening through completion of the study and to complete a pregnancy test at each study visit. The acceptable forms of contraception for this study include hormonal contraceptives (oral, implant, transdermal patch, or injection) at a stable dose for at least 1 month prior to screening, and barrier (condom with spermicide, diaphragm with spermicide). Sexual activity will be ascertained at each study visit for post-menarchal females and if sexually active, subject must verify use of the same 2 acceptable forms of contraception.
- Participants must be able to swallow cysteamine bitartrate DR capsules.
- Written informed consent from parent or legal guardian.
- Written informed assent from the child.

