7.2 Outcome measures

Primary outcome measure:

The primary outcome measure, improvement in NAFLD from the start of treatment to the end of treatment at 52 weeks, is defined for each patient as:

- Improvement in NAS score by 2 or more points, and
- No worsening of the fibrosis score

Secondary outcome measures:

- *Conversion from a diagnosis of NASH to not-NASH.* For the subset of patients with NASH at enrollment, determine the proportion whose 52-week liver biopsy results in a centrally determined histological diagnosis of not-NASH
- *Change in NAS*. Change in NAS, is defined for each patient, as the difference in 52 week vs. baseline NAS scores
- *Specific histologic features.* Changes in specific histological scores, defined for each patient, as the difference in 52 weeks vs. baseline, in the following histological features from centrally scores liver biopsies:
 - **o** Fibrosis
 - o Steatosis
 - Lobular inflammation
 - Portal chronic inflammation
 - **o** Ballooning

Change from stage 1b to 1a fibrosis. For the subset of patients with stage 1b fibrosis at baseline, determine the proportion whose 52-week liver biopsy results in a centrally determined histological diagnosis of fibrosis 1a.

• *Serum aminotransferase*. Change in serum aminotransferase, is defined for each patient, as the difference in 52 week vs. baseline serum aminotransferase

- *Gamma-glutamyl transpeptidase*. Change in serum gamma-glutamyl transpeptidase, is defined for each patient, as the difference in 52 week vs. baseline serum gamma-glutamyl transpeptidase
- *MRI-determined hepatic fat fraction*. Change in MRI-determined hepatic fat fraction is defined for each patient, as the difference in 52 week vs. baseline MRI-determined hepatic fat fraction
- *Markers of oxidation and anti-oxidant status*. Change in markers of oxidation and anti-oxidant status, is defined for each patient, as the difference in 52 week vs. baseline values of the following markers:
 - o Malondialdehyde,
 - o F2alpha-isoprostane,
 - o Total antioxidant capacity, and
 - Oxidized LDL
- *Fasting insulin.* Change in fasting insulin, is defined for each patient, as the difference in 52 week vs. baseline fasting insulin
- *Fasting glucose*. Change in fasting glucose, is defined for each patient, as the difference in 52 week vs. baseline fasting glucose
- *Obesity measures.* Change in obesity measures, is defined for each patient, as the difference in 52 week vs. baseline values of the following obesity measures:

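### Two secondary histology rules misclassify improvement: section 3.6 judges each feature by the total NAS, and the stage 1b outcome in 7.2 counts only an end stage of exactly 1a

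*Protocol*

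**What the plan says.** **Feature improvement.** Protocol section 3.6 names the outcome as "Changes in fibrosis, steatosis, lobular inflammation, ballooning, and other specific features from the histologic scoring system after 52 weeks of treatment compared to baseline". The next sentence gives the rule: "Improvement in specific features will be defined as any improvement in the NAS". Section 3.5 describes the NAS as "calculated as the sum of three components of the standardized histologic feature scoring system for liver biopsies": steatosis (0 to 3), lobular inflammation (0 to 3) and ballooning (0 to 2). The heading of 3.6 refers to section 7.2 for details. There the outcome is "Changes in specific histological scores, defined for each patient, as the difference in 52 weeks vs. baseline", listed for fibrosis, steatosis, lobular inflammation, portal chronic inflammation and ballooning. Section 7.2 does not say what counts as improvement in a feature.

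**Stage 1b.** Section 7.2 also sets a proportion whose denominator is given by "For the subset of patients with stage 1b fibrosis at baseline" and whose numerator is those "whose 52-week liver biopsy results in a centrally determined histological diagnosis of fibrosis 1a". Section 7.3 analyses binary secondary outcomes with a Mantel-Haenszel test stratified by clinic, and reads an odds ratio above 1 as favouring cysteamine.

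**The concern.** For the features, the rule in 3.6 ignores the feature it is meant to describe. Read literally, it gives every feature the same improvement rate, namely the share of children with any fall in NAS. A child whose fibrosis worsened could then be reported as having improved fibrosis. Section 3.5 says that ballooning and fibrosis carry prognostic meaning, so a wrong label on either one matters.

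For stage 1b, the outcome is read as a benefit, yet the best possible result (no fibrosis left) falls outside the numerator while the child stays in the denominator. That child is scored the same as one who did not change or who progressed.

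**Working it through.** No planning figure is at issue, so there is none to reproduce. The check sets the rules side by side and counts what they do.

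**(a) Total NAS against the feature's own score**

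Two examples show both kinds of error, using the components in section 3.5 (steatosis + lobular inflammation + ballooning):

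- Steatosis 3 to 2, inflammation 1 to 1, ballooning 1 to 1, fibrosis 1 to 2. NAS goes from 3+1+1 = 5 to 2+1+1 = 4, a fall. Under 3.6 every feature is improved, although two components did not change and fibrosis worsened.
- Steatosis 2 to 2, inflammation 1 to 2, ballooning 2 to 1. NAS goes from 2+1+2 = 5 to 2+2+1 = 5, no fall. Under 3.6 ballooning is not improved, although its own score fell.

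Full count: there are 4 × 4 × 3 = 48 possible component triples. Section 4.2 requires a baseline NAS of at least 4, which leaves 29 baseline triples. Pairing each with all 48 follow-up triples gives 29 × 48 = 1,392 pairs; the NAS falls in 858 of them.

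| Feature | NAS falls, feature not improved | of which feature worse | Feature improved, NAS does not fall | Classified differently |
|---|---|---|---|---|
| Steatosis | 306 of 858 (36%) | 116 | 132 | 306 + 132 = 438 of 1,392 (31%) |
| Lobular inflammation | 306 of 858 (36%) | 116 | 132 | 438 of 1,392 (31%) |
| Ballooning | 415 of 858 (48%) | 145 | 133 | 415 + 133 = 548 of 1,392 (39%) |

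For fibrosis and portal inflammation no count is needed, because the rule uses no information from either feature. The pairs are weighted equally, so the percentages show that misclassification is built into the rule. They do not predict how many children would be affected.

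**(b) Exactly 1a against any regression from 1b**

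The protocol gives neither the number of stage 1b children nor their expected shifts. The rates below are assumptions. Odds ratio = [p(active)/(1 − p(active))] ÷ [p(control)/(1 − p(control))].

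- Control: 10% to no fibrosis, 20% to 1a. Active: 25% to no fibrosis, 20% to 1a.
  - Exactly 1a: (0.20/0.80) ÷ (0.20/0.80) = 1.00.
  - 1a or none: (0.45/0.55) ÷ (0.30/0.70) = 1.91.
- Control: 10% and 25%. Active: 30% and 20%.
  - Exactly 1a: (0.20/0.80) ÷ (0.25/0.75) = 0.75.
  - 1a or none: (0.50/0.50) ÷ (0.35/0.65) = 1.86.
- Control: 5% and 20%. Active: 20% and 20%.
  - Exactly 1a: 1.00.
  - 1a or none: (0.40/0.60) ÷ (0.25/0.75) = 2.00.

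In the first and third cases the benefit disappears. In the second its direction reverses, because fewer active than control children end at exactly 1a.

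**The case against.** Section 3.6 is a summary that defers to 7.2, and 7.2 measures every feature on its own score. Section 7.3 analyses scores as continuous changes, and neither section lists a binary feature-improvement outcome. A reader might infer from 3.6 that the trial cannot say which feature changed. The documents do not support that, because the change analyses in 7.2 and 7.3 report each feature, fibrosis included, separately. This part of the objection stands and limits the harm to any improvement classification made under 3.6. It does not remove the error: 3.6 holds the only definition of feature improvement in the protocol. Even a generous reading, in which NAS means the feature's own component of it, cannot cover fibrosis or portal inflammation.

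On stage 1b, the outcome is titled as a change from 1b to 1a and measures just that; complete regression is still captured by the fibrosis-score change in the same section. The protocol does not print the fibrosis scale, so a category below 1a is an inference. It is a reasonable one: section 2.2 describes fibrosis as present only in some cases, and section 4.2 sets no fibrosis minimum for entry. A reader might also infer that the arm with deeper regression must score worse. That does not follow: in two of the three cases above the odds ratio is 1.00, and reversal needs fewer active children to stop at 1a. Nor do the documents suggest that large regression rates are likely. Sections 2.5.2 to 2.5.4 report no fibrosis improvement with metformin, pioglitazone or vitamin E, although those are other drugs. What remains is that a narrow title does not justify scoring full regression as non-response in an outcome read as benefit.

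**Conclusion.** Both points hold, for secondary outcomes only.

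(a) The rule in 3.6 conflicts with 7.2, cannot apply to fibrosis or portal inflammation, and misclassifies the three NAS components in 31% to 39% of possible score pairs. It affects any improvement label derived from it, not the continuous per-feature analyses.

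(b) The stage 1b outcome scores regression to no fibrosis as failure, assuming the scale has such a category. This can dilute a benefit and, under some stage shifts, reverse it. Its practical size is unknown, because the number of stage 1b children is not given and the shifts used here are assumed.

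The primary outcome, which already treats NAS and fibrosis as two separate conditions, and the sample size are untouched. The corrections should be made, but the main result does not depend on them.

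**What to change.** In section 3.6, replace the rule with: improvement in a specific feature is a decrease of at least 1 point in that feature's own score, and align the sentence with 7.2. In section 7.2, for children at stage 1b at baseline, count a 52-week stage of 1a or no fibrosis as success, and adjust the title of that outcome to match. Stating the fibrosis scale, including how 1a and 1b are coded, would make both rules unambiguous.

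The cost is two lines of wording. The biopsies are already scored centrally, so no new data, visits or participants are needed.

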4.1 Recruitment

Approximately 160 participants in 2 groups of equal size (80 per group) will be recruited at the clinical centers of the NASH CRN (averaging 16 patients per center) over a 19 month period.

Eligible patients will be identified and recruited at the participating clinical centers subject to the inclusion and exclusion criteria. Clinics will be expected to recruit sufficient overall numbers of minorities and females so that results can be generalized to these populations. Each clinic will develop a recruitment plan. These plans will vary from clinic to clinic depending on the available pools of patients and local recruitment resources and referral patterns.

4.2 Inclusion criteria

Patients must satisfy all of the following criteria to be eligible for enrollment:

- Children age 8-17 years inclusive.
- Liver biopsy within 90 days of screening visit and not more than 120 days before randomization.
- Clinical history consistent with NAFLD.
- Definite NAFLD based upon liver histology.
- No evidence of any other liver disease by clinical history or histological evaluation
- A histological severity of NAFLD Activity Score (NAS) \geq 4.
- Sexually active female participants of childbearing potential (i.e., not surgically sterile [defined as tubal ligation, hysterectomy, or bilateral oophorectomy) must agree to utilize the same two acceptable forms of contraception from screening through completion of the study and to complete a pregnancy test at each study visit. The acceptable forms of contraception for this study include hormonal contraceptives (oral, implant, transdermal patch, or injection) at a stable dose for at least 1 month prior to screening, and barrier (condom with spermicide, diaphragm with spermicide). Sexual activity will be ascertained at each study visit for post-menarchal females and if sexually active, subject must verify use of the same 2 acceptable forms of contraception.
- Participants must be able to swallow cysteamine bitartrate DR capsules.
- Written informed consent from parent or legal guardian.
- Written informed assent from the child.

